Rationale for Dose Selected

The daily doses selected (600 and 1200 mg) are consistent with those used in a recent large scale (N=433) efficacy and safety study of mifepristone for the treatment of psychotic depression¹⁷ which found no significant differences between mifepristone 600mg, 1200 mg and placebo for the percentages of patients with ≥ 1 adverse event or with serious adverse events. The most commonly reported side effects were: headache, dizziness and dyspepsia for mifepristone, and nausea and somnolence for placebo.

Rational for Study Duration

Dosing duration (1-week) provides a duration of drug exposure that is compatible with optimal drug effects for resetting the HPA axis and for maintaining subject safety.

Medication Supply

Mifepristone 300 mg tablets and matched placebo tablets will be provided by Corcept Therapeutics.

Medication Compliance

Subjects will receive a 1-week supply of double-blind study medication in a blister card package. Blistercards are consecutively numbered for each participant and prepared according to the randomization code. Neither subject nor study personnel involved in subject care or assessment will know the identity of the randomly assigned study drug. Medication will be identical in appearance and all subjects will be given the same number of double-dummy tablets to preserve the blind. Subjects will be instructed to take the study drug each morning, preferably with food, and to return the blistercard and any unused drug at the next visit (Week 1). A brief scripted phone call will be scheduled on Day 3 of medication to assess medication compliance, any AE's and subject concerns that could prompt study discontinuation. Compliance will be verified with returned medication package and pill count. Mifepristone plasma determinations will be obtained at Week 1 and will be analyzed retrospectively to verify correct medication assignment per the randomization code and ingestion of active medication and will be examined for an association with outcome.

Drug Accountability

All study medication is kept in a locked metal cabinet in the medication preparation room. The research technician labels and prepares the blinded medication in blistercards which are

identified by randomization code, and keeps a record of all medication dispensed and returned throughout the study.

Concomitant Pharmacological Treatments

Subjects will be instructed to not use any herbal, over-the-counter or prescribed medication without consulting the study physician, who will consult with the P.I. to determine the continued eligibility of the subject for participation in the study. All approved medications, e.g., NSAIDS or antihypertensives, will be recorded in the case report form with any changes recorded throughout the study.

Data and Safety Monitoring Plan

Potential risks and benefits for participants

Stringent procedures will be followed to minimize the risk of adverse reactions for participants, including the following:

- The P.I. is experienced and qualified to distinguish a serious adverse event (SAE) from a non-serious adverse event (AE). The P.I. will be responsible for monitoring the conduct of this single-site clinical trial to ensure the safety of participants and the integrity of the data. The P.I. will monitor subject side effect complaints, clinically significant lab abnormalities and findings on physical exam in consultation with study physicians and [name], MD, Pharm D, our independent Medical Safety Monitor, who has over a decade of experience as a Research Physician in the pharmaceutical industry involved in Phase I, II and III clinical trials. [name] will meet with members of her staff and the Medical Safety Monitor, [name], on a weekly basis to discuss progress of the study, subject enrollment and retention, the clinical status of active subjects and any safety issues as they arise.
- If a SAE occurs, the P.I., in consultation with the chief Study Physician, [name]., and the Independent Medical Safety Monitor, [name]., PharmD., will report it to the Scripps-IRB, our NIAAA Project Officer and the US FDA within 48 hours of becoming aware of the event. The written report will capture all safety information including the date of SAE onset, a description of the event, action taken, and whether a relationship between the SAE and drug exists. A summary of all AE's and SAE's that occurred during the previous year will be included in an annual progress report to the FDA, our NIAAA Project Officer and the Scripps-IRB.
- The study physician will be responsible for managing the SAE and/or making referrals for appropriate care, as needed, until the problem has resolved or stabilized with no further change expected, or is clearly unrelated to study medication, or results in death.
- Female subjects who are pregnant and nursing, or not using effective non-hormonal methods of birth control will be excluded from study.
- Participants who are found to require additional treatment at their follow up visit due to significantly increased alcohol consumption or serious psychiatric/medical symptoms will be offered referral for appropriate treatment. Treatment resources include the adjacent Scripps Green Hospital and Clinic where our study physicians have staff privileges and the nearby Scripps MacDonald's Center for Chemical Dependency that provides inpatient and outpatient services. We also provide referral to no-fee and sliding fee facilities.
- SAE's during follow up will be reported to the Scripps-IRB, our NIAAA Project Officer and the FDA within 48 hours of our becoming aware of the event, using the procedures for SAE's described above. All AE's and SAE's during follow up will be compiled in our annual reports to the Scripps-IRB, our NIAAA Project Officer and the FDA.

- Data forms and behavioral ratings for each subject will be formatted into a standardized case report form (CRF) upon which participants will only be identified by an assigned study number. Each CRF will be checked for accuracy and completeness. Data will be entered into a computerized database immediately after each subject completes the study. All data are routinely checked after entry, and distributional statistics are calculated and examined to identify outlying and/or potentially inaccurate data values and missing data. Data entry errors are promptly corrected and missing data verified with the CRF. All data are backed up on a nightly basis. Data will be stored and analyzed using computer facilities at the Laboratory of Clinical Psychopharmacology.
- Confidentiality will be preserved by the following measures: keeping CRF's in locked metal cabinets; CRF's and computerized data will be identified only by numerical code so that neither the subject's name nor initials will be used; the electronic database is password protected and accessible only to designated research personnel; no information will be released to non-study personnel regarding the identity or progress of subjects without written request by the individual subject to the Principal Investigator. A Certificate of Confidentiality will be applied for to protect against involuntary disclosure of the identities of research participants.

Stringent procedures will be followed to minimize the risk of adverse reactions for participants, including the following:

- *Study medication will be administered according to a protocol reviewed for safety by the FDA and conducted under an approved amendment to IND #114497 that we hold for our POC study in AUD.* The medication studied is considered safe when used in accordance with the procedures to be employed in the study.
- Subjects are required to be abstinent \geq 3 days prior to randomization and some subjects may be at risk for withdrawal. Withdrawal risk is evaluated at the screening visit with the Clinical Institute Withdrawal Assessment-Alcohol Revised (CIWA-AR). Subjects with CIWA scores \geq 9 are ineligible for randomization and referred for medical detoxification. However, our community dwelling subjects typically do not require medical detoxification, and are advised to reduce their alcohol intake incrementally such that 3 consecutive days of abstinence are achieved prior to their randomization (Week 0) visit. The CIWA-AR is then repeated at Week 0 to further rule out risk of significant withdrawal symptoms during double-blind treatment.
- Subjects will be excluded who are at increased risk through an extensive medical history, complete physical exam, including ECG, complete blood chemistry (CBC), liver function tests (LFT's), urinalysis, and urine toxicology screen for drug of abuse.
- Subjects with any conditions that would expose them to unusual risk (e.g., use of contraindicated medications, suicidal ideation, significant medical disorders *including prolongation of the QT_c interval*, or pregnancy) will be excluded.
- A menstrual history, 2 negative pregnancy tests, and birth control will be documented in women of childbearing potential, to avoid giving study drug to women with unrecognized pregnancies.
- Female subjects of childbearing potential will be informed that mifepristone may interfere with the effectiveness of hormonal contraceptives and will be required to use effective non-hormonal birth control for the 1-week duration of medication and for one month thereafter.
- Subjects will be advised neither to drive a car nor operate complex machinery until they have gained sufficient experience on drug to gauge whether or not it affects their mental and/or motor performance adversely.

- Subjects will be provided with their Study Clinician's business card and a copy of the informed consent that includes 24/7 phone numbers for study physicians.
- Participants will be asked about adverse events and concomitant medications at the scheduled phone call on Day 3 of medication and at each study visit.
- Participants will be instructed about signs and symptoms of adrenal insufficiency and how to contact the study physician in case they occur. The following language will be used in the informed consent:

Tell your doctor right away if you have any of these symptoms:

- * Unusual tiredness or weakness
- * Nausea and/or vomiting
- * Dizziness when standing
- * Aches and pains
- * Loss of appetite
- * Being depressed

- Female participants will be instructed to report unexplained vaginal bleeding.
- Participants reporting symptoms of adrenal insufficiency or unexplained vaginal bleeding during the 1-week of study medication will be discontinued from study drug and seen promptly for medical evaluation.
- Laboratory evaluations and electrocardiogram will be repeated at the conclusion of medication to identify any abnormalities potentially related to drug exposure. Any clinically significant abnormalities persisting at the end of medication will be followed by the investigator until resolution or until a clinically stable endpoint is reached.
- Participants will be evaluated at the end of study medication for:
 - Evidence of QT prolongation (ECG) and if present will be monitored until resolution
 - Signs and symptoms of adrenal insufficiency. If adrenal insufficiency is suspected, it will be followed-up closely. *We note that no case of adrenal insufficiency or QT prolongation has been reported in studies of similar duration and dosing (also see Darpo et al., 2013).*
- Following 1-week of study drug, subjects will be evaluated weekly through Week 8 and provided with manual-guided counseling, and will complete a follow up visit at Week 12. *Project MATCH found that 4 sessions of Motivational Enhancement Therapy (MET) in 12 weeks was as efficacious as 12 weekly sessions of Cognitive Behavioral Therapy or Twelve Step Facilitation for reducing drinking, leading to the conclusion that multiple types of behavioral interventions of varying intensity are equally helpful in early recovery.¹⁸ The manual-guided counseling we provide is most similar to MET. We chose 8 weeks of counseling and assessment based on the 8-weeks of aftercare and assessment in the 1-week mifepristone psychotic depression studies.^{17, 19, 20} Duration of mifepristone effects beyond 8-weeks has not been evaluated in controlled trials, but we will collect outcome data for Weeks 9, 10, and 11 by scheduled phone calls, and conduct an in person assessment at Week 12, in conjunction with referral for additional treatment if warranted.*
- Highly trained and experienced personnel will provide a degree of supervision that might not be available under usual treatment conditions.
- Subject clinical status will be carefully monitored by the P.I. and [name]., PharmD, Safety Monitor, during weekly laboratory meetings with all personnel involved in the study and by quarterly review of blinded tables of safety data, including rates per group of adverse events, serious adverse events and discontinuation due to adverse events, provided by our statistician. [name] will advise the PI and study physicians if trends emerge that warrant changes to the study protocol to protect the safety of research

participants. [name] will present any safety findings and proposed remedial actions to the Scripps-IRB and our NIAAA Program Officer.

- The clinical ratings and blood tests will be performed by experienced personnel to minimize complications and unnecessary fatigue and distress.
- The study physician will evaluate any subject experiencing clinical deterioration and make a clinically-based decision regarding study discontinuation and referral for appropriate care in consultation with the P.I. Criteria for study termination include: development of intolerable side effects; development or worsening of a physical or psychiatric disorder that requires treatment that would be in violation of the protocol. If a subject is discontinued, every attempt will be made to perform the evaluations specified for the final visit at the time of discontinuation. Reason(s) for premature termination will be documented in the case report form.
- At the follow-up visit, subjects who report significantly increased alcohol consumption or serious psychiatric/medical symptoms will be offered a referral to treatment specific to their needs.
- Importantly, the research group has a well-established record of subject safety in the conduct of analogous clinical trials and subjects will receive careful monitoring of their health status while in the study.

Risks to patient confidentiality will be mitigated by the following measures:

- Keeping the subject case report forms in locked metal file cabinets.
- Case report forms and computerized data will be identified only by numerical code so that neither the subject's name nor initials will be used.
- Access to computerized data will be password protected and available only to authorized study personnel
- No information will be released to non-study personnel regarding the identity or progress of subjects without written request by the individual subject to the P.I. In addition to the aforementioned protection of privacy, a Certificate of Confidentiality will be applied for to protect against involuntary disclosure of the identities of research participants.
- Published results will not reveal the identity of individual participants.
- *Confidentiality of genetic data will be protected including by coding and anonymization of samples and maintaining data under lock and key and limiting access to electronic data to authorized personnel. No genetic results will be communicated to study participants. The following language will be used in the informed consent to advise participants of available protections against discrimination based on genetic information obtained in this study, should confidentiality not be preserved:*
"A new federal law, called the Genetic Information Nondiscrimination Act (GINA), generally makes it illegal for health insurance companies, group health plans, and most employers to discriminate against you based on your genetic information. This law generally will protect you in the following ways:
 - *Health insurance companies and group health plans may not request your genetic information that we get from this research*
 - *Health insurance companies and group health plans may not use your genetic information when making decisions regarding your eligibility or premium*
 - *This new Federal Law does not protect you against genetic discrimination by companies that sell life insurance, disability insurance or long-term care insurance"*

Collection and Reporting of AEs and SAEs

The P.I. will be responsible for monitoring the conduct of this single-site human laboratory study to ensure the safety of participants. The P.I. will monitor subject side effect complaints, clinically significant lab abnormalities and findings on physical exam in consultation with study physicians and [name], MD, Pharm D, our independent Medical Safety Monitor, who has over a decade of experience as a Research Physician in the pharmaceutical industry involved in Phase I, II and III clinical trials. If a SAE occurs, the P.I., in consultation with the Study Physician, [name]., and the Independent Clinical Safety Monitor, [name]., PharmD., will report it to the IRB, our NIAAA Project Officer and the US FDA within 48 hours of becoming aware of the event. The written report will capture all safety information including the date of SAE onset, a description of the event, action taken, and whether a relationship between the SAE and drug exists. In addition, a summary of all SAEs that occurred during the previous year, and their outcomes, will be included in the annual progress report to the FDA, NIAAA and our IRB. AEs will be documented at each study visit on the Adverse Event case report form by recording of each adverse event and onset, duration, severity, relation to study medication and any clinical action. These will be compiled and reported to the FDA, NIAAA and our IRB in the annual progress report.

Management of SAEs or Other Study Risks

The study physician will be responsible for managing a drug-related SAE and/or making referrals for appropriate care, as needed, until the problem has resolved or stabilized with no further change expected, or results in death.

DSM Plan Administration

Responsibility for data and safety monitoring

The P.I. is responsible for monitoring this single-site human laboratory trial. [name] will meet with members of her staff and the Study Safety Monitor, [name], on a weekly basis to discuss progress of the study, subject enrollment and retention, the clinical status of active subjects and any safety issues as they arise.

Frequency of DSM

All case report form data will be entered into an electronic file on a daily basis as they are completed. Data safety monitoring will be conducted by the P.I. and Safety Monitor who will review adverse events on a weekly basis. The Safety Monitor will advise the P.I. and the study physicians if any changes in the study plan may be needed to improve subject safety.

Data safety and monitoring reports will be provided annually to the IRB, NIAAA and the FDA. We will use pre-established criteria and procedures for reporting AEs, SAEs, issues potentially arising from conflicts of interest significant protocol changes, and/or cause for trial termination to the IRB, NIAAA and the FDA.

DSM board plan

Per NIAAA guidelines, no DSM board is required for this single-site, early Phase II trial.

References

1. Miller WR. What is relapse? Fifty ways to leave the wagon. *Addiction*. 1996; 91(Suppl:S15-27).
4. Fertig J. NIAAA Clinical Investigations Group. Paper presented at Alcohol and Stress: A Framework for Future Treatment Strategies. May 2011; Volterra, Italy.

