A total of 150 subjects will be randomly assigned to 1 week of double-blind treatment with mifepristone 600 mg/d ($n=50$), 1200 mg/d ($n=50$) or placebo ($n=50$); all subjects will receive 8 weeks of counseling, 4 scheduled phone calls and a Week 12 follow up visit. Subjects will be medically healthy male or female volunteers, 18-65 years of age. Subjects must meet DSM-V criteria for current alcohol use disorder of moderate or greater severity, defined in DSM-V as ≥ 4 symptoms, because this is the level of severity likely to merit pharmacotherapy and to involve neuroadaptations in the stress systems that mifepristone is hypothesized to treat. Subjects must be abstinent ≥ 3 days (but ≤ 30 days) prior to randomization, as verified by the TLFB and BAC and have a CIWA ≤ 9 , to eliminate acute alcohol or withdrawal effects on study measures. Abstinence at randomization will be verified retrospectively by ethyl glucuronide/ethyl sulfate (EtG/Ets) testing, which can reliably detect alcohol metabolites in the urine 80 hours after alcohol consumption. EtG/Ets testing showed only 1 of 50 participants in our mifepristone lab study violated the 3-day abstinence requirement at baseline. Additionally, breathalyzer and Timeline Followback data are collected at every study visit; GGT data are collected monthly.

Inclusion Criteria:

- *Male or female volunteers, 18-65 years of age*
- *Meets DSM-V criteria for current alcohol use disorder of moderate or greater severity, defined by DSM-V as ≥ 4 symptoms*
- *In the month prior to screening, reports drinking > 21 standard drinks per week if male, > 14 if female, with at least one heavy drinking day (males: ≥ 5 drinks, females: ≥ 4 drinks) per week*
- *Seeking research-based outpatient treatment for AUD and willing to comply with the protocol, take daily oral medication for 1-week and complete 11 study visits*
- *Abstinent a minimum of 3 days (but not more than 30 days) prior to randomization*
- *Negative BAC and a CIWA score of ≤ 9 at randomization*
- *In acceptable health in the judgment of the study physician, on the basis of interview, medical history, physical exam, ECG, urine test and lab tests*
- *Females with childbearing potential must have a negative serum pregnancy test on the screening visit and a negative urine pregnancy test at randomization and agree to use non-hormonal effective birth control for the study duration and one month thereafter*

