This is a Phase II, single-site, randomized, double-blind, placebo-controlled, 3-arm, parallel groups, dose-ranging study of 1-week of treatment with mifepristone (0, 600, 1200 mg/d) given in conjunction with 8 weeks of manual-guided counseling, and a follow up visit at Week 12. Subjects will be 150 outpatient men and women seeking treatment for current AUD of moderate severity or greater, who are abstinent ≥ 3 and ≤ 30 days and not in acute withdrawal (CIWA ≤ 9) at time of randomization.

Initial Phone Screening: Clinically trained study personnel provide information about the study. Interested individuals who appear eligible are scheduled for a face-to-face intake evaluation.

Week -1, Screening: After providing written informed consent, subjects complete a Screening Visit for evaluation of eligibility (see Table 2). The Structured Clinical Interview for DSM-V (SCID-V) will be administered to determine the inclusion criteria of current AUD with ≥ 4 symptoms and to rule out AXIS I disorders that would warrant study exclusion. The subject's demographic information, medical and alcohol use history, and use of concomitant treatments will be recorded using standardized forms. Vital signs and breath alcohol concentration (BAC) will be assessed, and specimens for urinalysis, serum pregnancy test (if female), urine drug screen, blood chemistry that includes liver function tests (LFT's) and gamma glutamyl transferase (GGT), and complete blood count with differential (CBC w/diff) will be collected by the medical assistant and prepared for same day pick up by LabCorp for analyses. An electrocardiogram (ECG) will be performed. Subjects at risk of clinically significant symptoms of alcohol withdrawal (CIWA ≥ 9) are ineligible and will be referred for detoxification treatment. However, our community dwelling subjects typically do not require medical detoxification, and are advised to reduce their alcohol intake incrementally such that 3 consecutive days of abstinence are achieved prior to their baseline (Week 0) visit. The CIWA is then repeated at Week 0 to further rule out risk of significant withdrawal symptoms during double-blind treatment.

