Week 0, Randomization: Subjects complete evaluation for eligibility. Study physicians review all laboratory results, EKG's, vital signs, medical and alcohol histories, use of illicit substances and concomitant treatments, and perform a physical exam to medically clear an individual for admission to study. Medically cleared subjects complete baseline assessments and are randomized to receive a 1-week supply of double-blind drug.

Weeks 1-8: Subjects complete weekly study assessments and counseling described below and in Table 2. Subjects will be seen by the same study personnel and have their visits scheduled at

the same time of day (typically midday) across the study to avoid effects of uncontrolled sources of variance on study measures.

Weeks 9-11: Weekly phone calls are scheduled to maintain contact with the participant and obtain TLFB data.

Week 12: Subjects complete a follow up visit to assess persistence of treatment effects on outcome and safety assessments. *Procedures to maximize the likelihood of participation in the follow-up visit include: scheduled weekly phone calls to maintain contact with subjects, paying for the follow up visit, obtaining multiple back-up addresses and phone numbers, to assist in locating subjects. Patients who are found to have relapsed, or who display other clinically significant symptoms, will be offered referral for appropriate treatment.*

Table 2. Schedule of Procedures for Study Visits

Scheduled Procedures Week	-1	0	1	2	3	4	5	6	7	8	12
Informed consent, demographics, medical and alcohol history, SCID-V	X										
Alcohol Dependence Scale; Fagerstrom Test for Nicotine Dependence; Illicit Drug Use Index; Childhood Trauma Questionnaire; Treatment Goals Checklist	X										
BAC, Vital signs Adverse events, Concomitant Medications	X	X	X	X	X	X	X	X	X	X	
Pregnancy test ¹	X	X	X	X							
Clinical Institute Withdrawal Assessment-Revised (CIWA)	X	X									
CBC w/diff, blood chemistry ² , UA, UDS	X		X		X					X	X
ECG			X								
Plasma cortisol, ACTH		X	X	X		X				X	X
Mifepristone plasma concentration				X							
Alcohol Craving Questionnaire (ACQ); Timeline Follow Back Interview (TLFB); Pittsburgh Sleep Quality Index (PSQI); Beck Depression Inventory-II (BDI-II), State-Trait Anxiety Inventory (STAI)	X	X	X	X	X	X	X	X	X	X	
Neurocognitive Assessment, EtG/EtS			X								X
Physical exam, saliva and WBC for pharmacogenetics, dispense study drug			X								
Manual-guided counseling	X	X	X	X	X	X	X	X	X	X	

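### The CIWA cut-off for randomization is inconsistent at a score of exactly 9: the listed criteria admit it and the safety section appears to bar it

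*Combined protocol and SAP*

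**What the plan says.** All references are to the Combined protocol and SAP; the separate SAP is silent on both matters.

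**CIWA, limit that includes 9**
- Inclusion Criteria: "Negative BAC and a CIWA score of ≤ 9 at randomization".
- Subject Characteristics: abstinence "as verified by the TLFB and BAC and have a CIWA ≤ 9".
- Procedures, opening design statement: "not in acute withdrawal (CIWA ≤ 9) at time of randomization".

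**CIWA, limit that excludes 9**
- Data and Safety Monitoring Plan, on withdrawal risk: subjects whose score is greater than or equal to "9 are ineligible for randomization and referred for medical detoxification". The same bullet continues: "The CIWA-AR is then repeated at Week 0 to further rule out risk of significant withdrawal symptoms during double-blind treatment".
- Procedures, Week -1, Screening: those at risk of significant withdrawal ("CIWA ≥ 9) are ineligible and will be referred for detoxification treatment".

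**CIWA, other text**
- The description of the scale under Study Measures to Characterize the Sample covers Weeks -1 and 0 and gives a single level, 9 or above, at which drug treatment may be needed.
- The Exclusion Criteria contain no CIWA item.
- The Week 0 text has physicians review the records and "perform a physical exam to medically clear an individual for admission to study", but names no CIWA cut-off.

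**Birth control**
- Inclusion Criteria: women of childbearing potential must "agree to use non-hormonal effective birth control for the study duration and one month thereafter".
- The Exclusion Criteria and the Data and Safety Monitoring Plan tie the requirement to the single week of medication plus one month.

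**The concern.** Eligibility cut-offs should give one answer for each possible score. Here the answer for a 9 on the day of randomization depends on which section is consulted. The bar on a 9 lies outside the inclusion and exclusion lists, so staff who work only from those lists would randomize a subject whom the safety section appears to send for detoxification. At stake are consistent entry decisions and a safety screen for withdrawal before double-blind drug is started.

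The birth-control wording raises a smaller question of the same kind: how long women are asked to continue depends on the section read.

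**Working it through.** The plan states no figure to reproduce here. The check sets the rules side by side.

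**1. Where the CIWA rules collide.** For a score taken at Week 0, with the safety bar read as applying to randomization:

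| Week 0 score | Inclusion Criteria, Subject Characteristics, design statement (≤ 9) | Data and Safety Monitoring Plan (≥ 9 barred) |
|---|---|---|
| 8 or less | admitted | not barred |
| 9 | admitted | barred |
| 10 or more | not admitted | barred |

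The sets {≤ 9} and {≥ 9} share one integer, 9. Every other score gets the same answer from both rules.

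**2. Does a two-stage rule remove the conflict?** Suppose 9 or more bars at Week -1 only, and 9 or less suffices at Week 0. The collision then disappears, because the rules apply to different visits. Against that reading:
- The safety section attaches its bar to randomization, not to passing screening.
- It describes the Week 0 repeat as further ruling out the same risk and gives no new threshold. Under a two-stage rule the repeat would be one point looser than the first test.
- The scale description gives one level for both visits.
- No section says that two cut-offs are intended.

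**3. Where the bar is recorded.** The only CIWA item in the two lists is the inclusion criterion, which speaks of randomization and includes 9. A bar at 9 appears only in the Week -1 procedures and the safety section, whichever visit it is meant for. The amendment request that can be read concerns removal of the lower dose arm and alters neither rule.

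**4. Birth-control periods.** Count from Week 0 and take one month as 30.4 / 7 = 4.3 weeks (assumption).
- Medication week plus one month: 1 + 4.3 = 5.3 weeks.
- Study duration plus one month, if the study ends at Week 12: 12 + 4.3 = 16.3 weeks. Gap 16.3 − 5.3 = 11 weeks.
- The same, if it ends at Week 8: 8 + 4.3 = 12.3 weeks. Gap 12.3 − 5.3 = 7 weeks.

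The month cancels, so the gap depends only on where the study is taken to end, which the protocol does not define. Table 2 has 1 + 1 + 8 + 1 = 11 visits (Weeks -1, 0, 1 to 8, and 12), which matches the 11 visits in the Inclusion Criteria and points to Week 12. On the other side, Week 12 is called a follow-up visit, and the payment text names study and follow-up separately.

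**The case against.** The strongest reply is the two-stage reading. In the safety section, the sentence barring scores of 9 or more comes straight after one about the screening visit. It is followed by advice to cut down before Week 0, and only then by the repeat test. The sequence closely tracks the Week -1 text in Procedures. On that view, being barred from randomization is simply the consequence of the screening score. The scale description is no help against this, since it explains the instrument and sets no entry rule. This much stands: the text is open to that reading, and a reader who infers that the safety section flatly rules it out goes further than the words allow. What does not follow is that the protocol is clear. The two-stage rule has to be supplied by the reader, and the literal bar on randomization remains the more natural sense.

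A second reply is that little turns on it. Applying every section together excludes a 9, so nobody is compelled to randomize one. Abstinence of at least 3 days, a negative BAC and physician clearance also apply. That is fair, and it limits the weight of the point. It does not settle which rule governs, because the protocol gives no order of precedence between sections.

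On birth control, a reader might infer a contradiction, or that women were told to stop too early. Neither is supported. Inclusion and exclusion criteria must both be met, so the longer period governs entry and contains the shorter one. The consent text is not available, so what women were told cannot be checked.

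**Conclusion.** The CIWA cut-off for randomization is inconsistent at a score of exactly 9. The listed criteria and design statement admit it; the safety section, on its more natural reading, bars it. A deliberate two-stage rule is possible but nowhere stated. The extent is one integer score; the documents do not say how many subjects scored 9 at Week 0, and there is no evidence that any such subject was randomized. It would be too strong to conclude that the protocol requires randomizing someone it also refers for detoxification.

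The birth-control wording is a minor mismatch between nested periods. The gap is about 7 weeks if the study is taken to end at Week 8 and about 11 if at Week 12.

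Neither matter affects sample size, power or the efficacy analysis. The first should be corrected because it is an entry rule with a safety purpose. This review takes no view on which cut-off or period is right.

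**What to change.** - **CIWA.** Reconcile Subject Characteristics, the Inclusion Criteria, the Procedures design statement, the Week -1 text and the Data and Safety Monitoring Plan to one explicit rule whose admitting and barring ranges do not overlap. Check the scale description against it. State whether the rule applies at screening, at Week 0 or at both; if two cut-offs are intended, say so and give each. Put the rule in the eligibility criteria and in any checklist drawn from them. The sponsor's clinicians choose the value.
- **Birth control.** State one period, with a defined end point chosen by the sponsor's clinicians, in the Inclusion Criteria, the Exclusion Criteria and the safety section.

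The cost is protocol wording and a checklist update. Nothing changes in sample size, power or the efficacy analysis.
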